7.1 Therapeutic Parameters

1. Prestudy scans and x-rays used to assess all measurable or non-measurable sites of disease must be done within **4 weeks** prior to randomization/registration.
2. Prestudy CBC (with differential and platelet count) should be done \leq **4 weeks** before randomization/ registration.
3. All required prestudy chemistries, as outlined in Section [1.6](#), should be done \leq **4 weeks** before randomization/registration – unless specifically required on Day 1 as per protocol.
4. The diagnostic bone marrow aspirate must be obtained within two weeks prior to randomization.
5. The required prestudy chemistries, as enumerated in Section [3](#), should be obtained within forty-eight hours prior to randomization. Please note that the dose of daunorubicin is adjusted, for cycle 2 induction only, based upon the total bilirubin as indicated in Section [5.4.2](#).
6. Prestudy CBC should be repeated \leq 48 hours prior to randomization.
7. The cardiac ejection fraction will be determined prior to induction chemotherapy, and prior to re-induction (if required). The cardiac ejection fractions should be determined by either MUGA or echocardiography throughout the study.

Rev. 2/12

Rev. 8/13

Rev. 2/13.
7/14

	Induction & Re-Induction			Consolidation I and II		Maintenance Observation vs. Decitabine	Follow-Up		
	Prior	Daily	Weekly	Prior	Daily		Monthly	Quarterly	Annually
History and Physical	X	X ¹		X ¹	X ¹	X ²	X ¹²		
Weight, Height (baseline)	X	X ¹		X ¹	X ¹				
CBC	X ¹	X ¹		X ¹	X ¹	X ²	X ¹⁶		
HLA Typing	X ¹¹								
Serum Potassium, Calcium, Creatinine, Serum Phosphorus, Serum Uric Acid		X ¹⁰							
Serum Creatinine, Uric Acid, Bilirubin, SGPT, (ALT) LDH, Alk Phosphatase, SGOT (AST) Mg	X	X ³	X ³	X ³	X ³				
EKG	X			X					
Bone Marrow Aspirate, Biopsy and Cytogenetics ^{9,4}	X		X ⁴	X ¹⁹		X ⁸		X ¹⁷	X ¹³
Cardiac Ejection Fraction (MUGA/Echocardiogram)	X ^{5,7}			X ⁷		X ⁷			
Cerebellar Neuro Checks					X ⁶				
QOL ¹⁴	X	X ¹⁵				X			
Geriatric Assessment ¹⁸	X								
ALESE Questionnaire	X ²⁰								

- 1 The daily evaluations should be performed until discharge from the hospital. If the patient is discharged prior to recovery of ANC or platelet count the values should be obtained no less than twice weekly until the outcome BM is performed
- 2 It is required that complete blood counts be obtained every 4 weeks for the first twenty-four months after the conclusion of consolidation therapy. Complete blood counts should be obtained every three months in the third year. The frequency in subsequent years is at the discretion of the investigator.
- 3 During the administration of daunorubicin or high-dose cytarabine the serum creatinine and total bilirubin are required daily to adjust dose of medications. After the administration of chemotherapy the values must be determined and reported at least weekly or more frequently as clinically indicated.
- 4 A bone marrow is required on day 12-14 (+/- 1 day) to assess whether the patient has achieved an aplastic BM and will receive GM-CSF or G-CSF or a repeat course of induction. Subsequent marrows until recovery of peripheral blood counts are at the discretion of the treating physician. An outcome BM must be performed no sooner than day 28 and no later than day 56 to determine response to induction therapy at the time of recovery of ANC to >1000 & platelets (>100,000) or if the patients is suspected to have residual AML, or if no further recovery is expected (e.g. plateau in platelet recovery).
- 5 If the cardiac ejection fraction cannot be obtained due to weekend or holiday then patients may be enrolled provided there are no clinical signs or there is no history of significant cardiovascular disease and a measurement of cardiac ejection fraction will be performed within 5 days of study enrollment.

6 Prior to each dose of cytarabine during consolidation for patients randomized to Arms A and C.

Rev. 2/13 7 The Cardiac Ejection Fraction must be measured prior to Induction. For patients on Arm A, a repeat measurement is recommended before receiving re-induction (if indicated). Repeat measurement prior to Consolidation Cycle 1 (Arms C & D) is recommended per institutional guidelines and as clinically indicated. **For patients who proceed to Arm G (Allogeneic stem cell transplantation) a repeat measurement of Cardiac Ejection Fraction must be performed after recovery from last cycle of chemotherapy and prior to start of transplant conditioning regimen**

Rev. 2/12 8 Routine bone marrow aspirate and biopsy is required every 3 months during maintenance and observation (Arms E and F) for first 24 months.

Rev. 2/13 9 A repeat bone marrow to confirm the maintenance of a CR prior to Consolidation II is not required provided a complete blood count with differential and platelet count remains within the range anticipated during a CR. Bone marrow (or peripheral blood if bone marrow is unavailable) should be sent to the institution's local cytogenetics laboratory for analysis. Please refer to the table in Section [7.3](#) for the time points for the submission of karyotypes for central review.

10 Monitoring for tumor lysis syndrome at the initiation of induction therapy is strongly suggested at least every 8-12 hours for at least the first 3-5 days of treatment, and at further intervals at the discretion of the investigator.

Rev. 2/13 11. HLA -typing (Class I & Class II) should be performed prior to therapy on all patients and on siblings who are eligible donors. The number of full siblings with ages and reason for ineligibility (including refusal) must be noted.

12. Physical only

13. If clinical or hematological evidence of relapse.

Rev. 8/13 14. QOL must be presented to all patients that consented to the QOL component at the following time points:

12/13

- Baseline before induction. (Beginning Step 1)
- At day 14 (+/- 2 days) following 1st induction. (Nadir of Step 1)
- Following the outcome restaging BM (day 35-56) prior to consolidation therapy. (End of Step 1, beginning Step 2)
- At the beginning of randomization to Arm E or F. (Beginning of Step 3)
- At the end of the observation/maintenance decitabine (i.e. after 12 months after randomization to Arm E or F). (End of Step 3)

NOTE: QOL is also to be assessed at the time a patient is removed from or elects to withdraw from the study.

Rev. 12/13, 7/14 15. QOL should be done at day 14 nadir and following the outcome restaging BM (day 35-56). These must be presented to all patients that consented to the QOL component of the protocol.

16. Monthly after 2nd randomization for 2 years, every 3 months for 2 years, every 6 months for a year and annually afterwards up to five years.

17. A surveillance BM aspirate and biopsy every 3 months for 2 years beginning at the time of the second randomization, and after that, when clinically indicated (e.g., symptoms of relapse or abnormal CBC).

18. Geriatric Assessment will be measured at Baseline before Induction.

19. BM required prior to consolidation cycle 1 only.

Rev. 2/13 20. ALESE: "Acute Leukemia Epidemiology and Survival in ECOG-ACRIN" Questionnaire should be administered early during induction therapy, preferably in the first week whenever possible. (See Section [1.6.6](#), [6.8](#), and [Appendix V](#)). For instructions on returning the questionnaire, please refer to [Appendix V](#), page 34.

7.2 **Arm G Only (Allogeneic Stem Cell Transplantation)**

	Prior to AlloSCT	Twice a week to Day +28 Weekly to Day +100 Monthly to Day +365	Restaging*	Post-treatment Follow-Up**
Tests & Observation				
History & Progress Notes	X	X	X	X
Physical Examination	X	X	X	X
Vital Signs & Weight	X	X	X	X
BSA	X			
ECOG PS	X	X	X	X
Toxicity Assessment		X	X	X
QOL ¹				
Lab Studies				
CBC, Diff, Plts	X	X	X	X
Serum creatinine, BUN	X	X		X
Creat. Clearance & Urinalysis	X			
Serum Electrolytes	X	X		
AST, Alk Phos, Bilirubin	X	X		X
Total Protein, Albumin	X			
EKG	X			
MUGA or Echo	X			
PFT (Lung Function)	X			
Hepatitis screen, CMV, HIV, EBV, HSV	X			
CMV Ag or PCR		A		
Tacrolimus		D		
Serologies & HLA Typing (donor & recipient)	X			
Staging				
CXR (PA/Lat)	X			
BM Asp. & Biopsy	X		C	X ²
Chimerism Samples (+/- 7 days)	B	B	B	B

* Restaging will occur between days +90-100, and +150-180, then q3 months for the 1st year.

** After restaging, at least q6 months for a maximum of 5 years from AlloSCT.

1. QOL will be performed at the following time points: At the beginning of the conditioning regimen and 100 days (+/- 14 days) post transplant- TOTAL 2 time points.

2. Within 1 month after Allo SCT
 - A Weekly beginning day +7 through day +100, then every other week until day +180.
 - B Samples to be collected prior to study (from both donor & recipient), and from recipient on days+30, +60, +90, +120, +180, +270, +365, and at relapse.
 - C BM aspirate & biopsy (& cytogenetics & flow cytometry) will be required at days +90-100, and day +150-180, then q3 months for 2 years, then as clinically indicated.
 - D Twice weekly beginning days -2 until day+28, then weekly until day +150 or until drug stopped.

Rev. 2/12, 8/13, 7/14 7.3 **Biological Sample Submissions**

Rev. 2/13, 12/13

1. Peripheral blood, bone marrow, and smears must be submitted for centralized immunophenotyping during pre-registration for eligibility testing
2. Karyotypes must be submitted at baseline for central review as outlined in Section [10](#).
3. Follow-up karyotypes, smears, bone marrow, and peripheral blood must be submitted for review.
4. Peripheral blood and buccal swabs/rinse are to be submitted for banking per patient consent.

Rev. 12/13

Rev. 12/13

NOTE: It is required that biological sample submissions be logged into the ECOG-ACRIN Sample Tracking System (STS) (see Section [10.6](#)) for purposes of monitoring compliance.

Rev. 12/13		Pre-registratioin	Step 1 - Randomization (Baseline) ¹	Time of Outcome Following Induction (Prior to Consolidation) ⁸	End of Consolidation (Prior to 2 nd Randomization - Step 3) ⁴	Relapse	Send To
MANDATORY – Submissions required for central review							
	Karyotypes		X	X	X	X	Cyto lab ²
Rev. 2/13	Bone Marrow/ Peripheral Blood Smears (Wright-Giemsa stained)	X		X	X	X	
	Bone Marrow Aspirate (heparin, FIRST PULL) ^{6,9}	X		X	X	X	LTSL ³
	Peripheral Blood (heparin, green or EDTA purple top tubes, (4) 10 mL tubes, 30-40 mL) ⁶	X		X	X	X	
From patients who answer “YES” to “I agree to provide additional specimens for research.”							
	Peripheral Blood (red top tubes, (2) 10 mL tubes, 15-20 mL)		X	X	X	X	LTSL ³
	Buccal Rinse (preferred) or Swab ⁷		X				LTSL ³

Rev. 12/13

1. Pre-study bone marrow, peripheral blood, and smears must be submitted for centralized immunophenotyping to determine patient eligibility. This testing is mandatory for participation in this study.
2. Submit to the ECOG-ACRIN Cytogenetic laboratory at Mayo Clinic.
3. Submit to the ECOG-ACRIN Leukemia Translational Studies Laboratory (LTSL). Signed E2906 patient consents and HIPAA authorizations must be submitted to the LTSL prior to or at time of submission of pre-registration specimens to the LTSL.
4. At time of evaluation response.
5. [Deleted in Addendum #8]

Rev. 2/13, 8/13, 12/13

6. Bone marrow and peripheral blood will also be used for the optional correlative studies per patient consent.

Rev. 12/13

7. Buccal rinse (preferred) or swabs are strongly encouraged to be collected at baseline, but can be collected at any other time during the study, if necessary.

Rev. 12/13

8. At time of response assessment or off-study, whichever occurs first.

9. The laboratory will accept any amount as long as it represents a first pull. It is imperative that aspirate from a separate first pull be submitted. DO NOT SUBMIT THE SECOND OR THIRD PULL OF ASPIRATE FROM THE SAME ASPIRATION SITE.

8. Drug Formulation and Procurement

8.1 Cytarabine

8.1.1 Other Names

Cytosar-U® Ara-C, Arabinosyl, cytosine arabinoside.

8.1.2 Classification

Antimetabolite.

8.1.3 Mode of Action

Converted to cytarabine triphosphate (Ara-CTP), a competitive inhibitor of DNA polymerase. The drug is also incorporated into cellular DNA and RNA. It is active against cells in S-phase and is considered to be phase specific.

8.1.4 Storage and Stability

The dry powder is stored at room temperature. Solutions reconstituted with sterile water without preservative should be used immediately; solutions reconstituted with Bacteriostatic of Water are stable up to 48 hours at controlled room temperature (15° to 30°C). Solutions with a slight haze should be discarded.

8.1.5 Dose Specifics

Induction Arm A

100 mg/m²/day by 24 hour continuous infusion for 7 days (days 1-7).

Consolidation I

1500 mg/m² as a one hour intravenous infusion every 12 hours for a total of 12 doses (days 1-6) for patients < 70 years of age, or a total of 6 doses for patients ≥ 70 years of age. See Section [5.4.1](#) for dose modifications for Consolidation I. See Section [5.6.3](#) for duration of Consolidation II therapy.

8.1.6 Preparation

For IV use, reconstitute the 100 mg vial with 5 mL bacteriostatic water for injection to achieve a concentration of 20 mg/mL. Add 10 mL of bacteriostatic water to the 500 mg vial to achieve a final concentration of 50 mg/mL. Add 10 and 20 mL of bacteriostatic water to the 1 and 2 gm vials respectively to achieve a final concentration of 100 mg/mL. For subcutaneous use, reconstitute the powder with sterile water or saline to a concentration of 50-100 mg/mL. For IT use, mix with lactated Ringer's solution or normal saline without preservatives.

8.1.7 Administration

IV push, IV continuous infusion, subcutaneous, or IT. Cytarabine is not absorbed when given orally.

8.1.8 Incompatibilities
Possible interaction with fluorouracil.

8.1.9 Compatibilities
Cytarabine (0.25 mg/mL), daunorubicin (0.03 mg/mL) and etoposide (0.4 mg/mL) are stable in D5/0.45% NaCl for 72 hours at room temperature. Cytarabine is also compatible with sodium chloride, potassium chloride, calcium, and magnesium sulfate.

8.1.10 Availability
Commercially available in 100 mg, 500 mg, 1 gm, and 2 gm vials.

8.1.11 Side Effects

1. Hematologic: Leukopenia, thrombocytopenia, anemia, and phlebitis. Nadir occurs in 5-7 days with recovery in 2-3 weeks.
2. Dermatologic: Rash, alopecia.
3. Gastrointestinal: Nausea, vomiting, diarrhea, dysphagia, mucositis, anorexia.
4. Hepatic: Transient increase in liver enzymes.
5. Renal: Urinary retention.
6. Other: Flu-like syndrome, fever. Profound hyperuricemia may occur in leukemia patients with high white blood counts. Conjunctivitis, dizziness, shortness of breath, headache, urticaria, pruritis, abdominal pain, pericarditis.
7. After intrathecal administration, the most common side effects are nausea, vomiting, fever, and headache, usually mild and self-limiting. Meningism, paresthesia, paraplegia, seizures, blindness, necrotizing encephalopathy have occurred.

8.2 Daunorubicin

8.2.1 Other Names
Daunomycin, Rubidomycin, Cerubidine.

8.2.2 Classification
Anthracycline antibiotic.

8.2.3 Mode of Action
Anthracycline mechanism of action results in a very tight binding of the drug to the DNA molecule. The ultimate effect is interference with nucleic acid synthesis, both RNA and DNA.

8.2.4 Storage and Stability
Intact vials are stored at room temperature and protected from direct sunlight. Reconstituted solutions are stable for 48 hours when refrigerated and 24 hours at room temperature, when protected from sunlight.

8.2.5 Dose Specifics Induction Arm A
60 mg/m²/day by 10-15 minute intravenous infusion for 3 days (days 1, 2 and 3).
NOTE: No dose modification during initial induction. See Section [5.4.2](#) for dose modification during induction cycle II.
Doses should be reduced in presence of impaired hepatic or renal function. Patients with serum bilirubin of 1.5 to 3 mg/dl should receive 75% of the usual dose; patients with serum bilirubin or serum creatinine 3.1 to 5 mg/dl should receive 50% of the usual dose.

8.2.6 Preparation
Each 20 mg vial is reconstituted with 4 mL of sterile water to give a final concentration of 5 mg/mL. The desired dose is drawn into a syringe containing 10-15 mL of normal saline. Protect from sunlight.

8.2.7 Administration
10-15 minute intravenous infusion.

8.2.8 Incompatibilities
Sodium heparin.

8.2.9 Availability
Commercially available in 20 mg glass vials of red colored lyophilized drug. Also available in 50 mg vials.

8.2.10 Side Effects

1. Hematologic: Myelosuppression (leukopenia with a nadir between 1-2 weeks).
2. Dermatologic: Rash; alopecia; chemical thrombophlebitis or local necrosis if extravasation occurs.
3. Gastrointestinal: Nausea, vomiting, commonly occurring one hour after a dose and lasting for several hours; diarrhea, stomatitis.
4. Cardiovascular: Arrhythmias, usually transient; congestive cardiomyopathy; maximum total (lifetime) dose of 500-600 mg/m² is recommended because of cumulative cardiotoxicity.
5. Renal: Red urine; not hematuria.
6. Other: Fever; transient elevations in serum bilirubin, AST, alkaline phosphatase.

8.2.11 Nursing Implications

1. Vesicant - avoid extravasation. Refer to extravasation protocol if inadvertent infiltration occurs.
2. Monitor CBC, platelet counts.
3. Advise patient of red coloration of urine.
4. Administer antiemetics as needed.

8.3 Decitabine

8.3.1 Other Names

Dacogen®, 5-aza-2'-deoxycytidine, 5-aza-CdR

8.3.2 Classification

Antineoplastic, DNA hypomethylating agent

8.3.3 Mode of Action

A cytosine nucleoside analog. The drug inhibits DNA methyltransferase at low doses promoting DNA hypomethylation and reactivation of previously silenced genes. At higher doses, the drug has a direct cytotoxic effect. It is an S-phase specific agent.

8.3.4 Storage and Stability

Intact vials are stored at room temperature. Unless used within 15 minutes of reconstitution, diluted decitabine solution must be prepared using cold (2° to 8°C) infusion fluids and stored at 2° to 8°C for up to a maximum of 7 hours until administration.

8.3.5 Dose Specifics

Decitabine 20 mg/m²/day IV over 1 hour QD x 3 days, repeated Q 4 weeks x 12 months total. See Section [5.4.3](#) for duration.

In the absence of a hypoplastic marrow (5% or less cellularity), clearly progressive increase in bone marrow blast count, febrile neutropenia, or unresolved systemic neutropenic infection, dosing should be continued at the recommended dose without delay. In the event of delayed recovery to pre-dose ANC and platelet counts for more than two cycles, the dose should be reduced by approximately 25% upon restarting therapy.

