3.2.8 Maintenance Criteria, Step 3 for Arms E and F

3.2.8.1 Maintenance should commence within 60 days of recovery of peripheral blood counts after Consolidation Cycle 2. Patients must begin Consolidation Cycle 2 within 60 days of recovery to be eligible for further therapy.

3.2.8.2 Patients must have maintained peripheral blood evidence of a remission as defined in Section [6](#) and must have a CR or CRi, confirmed on restaging BM aspirate and biopsy and cytogenetic analysis.

3.2.8.3 Patients must have an ECOG performance status of 0 -2.

3.2.8.4 Patients must have resolved any serious infectious complications related to Consolidation Cycle 2.

3.2.8.5 Any significant medical complications related to Consolidation Cycle 2 must have resolved.

3.2.8.6 Patients must have a total serum bilirubin \leq 1.5 x ULN and a serum creatinine \leq grade 1. The values must be obtained within 48 hours prior to randomization.

NOTE: If total bilirubin is 2-3 mg/dL, but direct bilirubin is normal, then the patient will be considered eligible.

3.2.8.7 The ANC must be $>$ 1000 mm³ and the platelet count $>$ 75,000 mm³ prior to starting every cycle of treatment with decitabine. Decitabine may be delayed for up to 4 weeks between cycles (i.e. may be administered as infrequently as q8 weeks) while waiting for counts to recover.

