5.1.8 Maintenance

5.1.8.1 Observation vs. Decitabine Maintenance (2nd Randomization) – Arm E and Arm F

Patients who complete consolidation therapy will undergo restaging with a BM aspiration & biopsy and repeat BM cytogenetics to confirm CR or CRI. Patients will then be randomized to maintenance therapy with decitabine vs. monthly observation for 12 months.

- Decitabine 20 mg/m²/day IV over 1 hour QD x 3 days, repeated Q4 weeks x 12 months total⁷⁵, up to 13 cycles, but not to continue beyond 12 months. Regardless of treatment delays, the total duration of maintenance therapy will be 12 months.
- There are no planned dose reductions in decitabine. Patients unable to receive treatment on schedule (i.e. planned q4 weeks, but delays up to 4 weeks allowed) due to cytopenias or persistent side effects will discontinue decitabine and subsequently be observed per the 'observation' group (Arm E), although they will be analyzed on an 'intention to treat' basis as having been assigned to Arm F.
- The ANC must be > 1000 mm³ and the platelet count > 75,000 mm³ prior to starting every cycle of treatment with decitabine. Decitabine may be delayed for up to 4 weeks between cycles (i.e. may be administered as infrequently as q8 weeks) while waiting for counts to recover.
- Monthly CBC and examination will be performed on all patients assigned to decitabine or observation for 24 months

Rev. 8/13

5.1.8.2 Patients who do not meet eligibility for Randomization to Observation vs. Decitabine Maintenance after recovery from Consolidation should be followed according to Arm E.

5.2 **Adverse Event Reporting Requirements**

5.2.1 **Purpose**

Adverse event data collection and reporting, which are required as part of every clinical trial, are done to ensure the safety of patients enrolled in the studies as well as those who will enroll in future studies using similar agents. Adverse events are reported in a routine manner at scheduled times during a trial (please refer to the E2906 Forms Packet for the list of forms with directions for routine adverse event reporting). Additionally, certain adverse events must be reported in an expedited manner for more timely monitoring of patient safety and care. The following sections provide information about expedited reporting.

5.2.2 **Determination of Reporting Requirements**

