The Comprehensive Adverse Events and Potential Risks List (CAEPR) provides a thorough and detailed list of reported and/or potential adverse events associated with the Decitabine. The CAEPR is developed and continuously monitored by the CTEP Investigational Drug Branch (IDB). The information listed in the CAEPR below, as well as the other resources described in the 'Determination of reporting requirements' part of the Adverse Event Reporting section in this protocol, can be used to determine expectedness of an event when evaluating if the event is reportable via CTEP-AERS. Frequency is provided based on 1658 patients. Below is the CAEPR for Decitabine (5-aza-2'-deoxycytidine).

Rev. 7/14

Rev. 12/13,
5/17

Version 2.4, January 4, 2017¹

Adverse Events with Possible Relationship to Decitabine (5-aza-2'-deoxycytidine) (CTCAE 4.0 Term) [n= 1832]		
Likely (>20%)	Less Likely (<=20%)	Rare but Serious (<3%)
BLOOD AND LYMPHATIC SYSTEM DISORDERS		
Anemia		
	Febrile neutropenia	
GASTROINTESTINAL DISORDERS		
	Abdominal pain	
	Anal mucositis	
	Constipation	
	Diarrhea	
	Mucositis oral	
Nausea		
	Rectal mucositis	
	Small intestinal mucositis	
	Vomiting	
GENERAL DISORDERS AND ADMINISTRATION SITE CONDITIONS		
	Chills	
	Edema limbs	
Fatigue		
Fever		
	Non-cardiac chest pain	
	Pain	
IMMUNE SYSTEM DISORDERS		
	Autoimmune disorder	
INFECTIONS AND INFESTATIONS		
Infection ²		
INJURY, POISONING AND PROCEDURAL COMPLICATIONS		
	Bruising	
INVESTIGATIONS		
	Alanine aminotransferase increased	
	Aspartate aminotransferase increased	
	Blood bilirubin increased	
	Creatinine increased	

	Lymphocyte count decreased	
Neutrophil count decreased		
Platelet count decreased		
White blood cell decreased		
METABOLISM AND NUTRITION DISORDERS		
	Anorexia	
	Hyperglycemia	
	Hyperuricemia	
	Hypoalbuminemia	
	Hypocalcemia	
	Hypokalemia	
	Hypomagnesemia	
	Hyponatremia	
MUSCULOSKELETAL AND CONNECTIVE TISSUE DISORDERS		
	Arthralgia	
	Back pain	
	Bone pain	
	Pain in extremity	
NERVOUS SYSTEM DISORDERS		
	Dizziness	
	Headache	
		Intracranial hemorrhage
	Somnolence	
PSYCHIATRIC DISORDERS		
	Anxiety	
	Insomnia	
RESPIRATORY, THORACIC AND MEDIASTINAL DISORDERS		
	Cough	
	Dyspnea	
	Laryngeal mucositis	
	Pharyngeal mucositis	
	Pharyngolaryngeal pain	
	Respiratory hemorrhage ³	
	Tracheal mucositis	
SKIN AND SUBCUTANEOUS TISSUE DISORDERS		
	Alopecia	
	Pruritus	
	Purpura	
	Rash maculo-papular	
VASCULAR DISORDERS		
	Hematoma	
	Phlebitis	
	Vascular disorders - Other (hemorrhage with decreased platelets)	

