5.4.3 Decitabine Arm F Maintenance

There are no planned dose reductions in decitabine. Patients unable to receive treatment on schedule (i.e. planned q4 weeks, but delays up to 4 weeks allowed) due to cytopenias or persistent side effects will discontinue decitabine and subsequently be observed per the 'observation' group (Arm E), although they will be analyzed on an 'intention to treat' basis as having been assigned to Arm F.

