9.8 Correlative Studies

The first goal of the correlative studies is to perform expression and methylation profiling on all patients receiving decitabine and to correlate their integrated epigenetic signatures with response to decitabine. The second goal is to examine the epigenetic profiles of remission marrow in patients randomized to observation vs. decitabine in E2906 to determine whether the epigenetic signature of apparently morphologically normal bone marrow is predictive of relapse or response to decitabine maintenance. These analyses will be exploratory in nature. Assume that 86 patients will receive decitabine maintenance treatment and 86 patients will be randomized to the observation arm. Among them, 45%-50% will submit samples and have sufficient material for expression and methylation profiling. Genomic microarrays will be used to study DNA methylation, and gene expression arrays will be used to study expression. Both types of arrays are made by the NimbleGen company. The assay for DNA methylation is HELP (HpaII tiny fragment enrichment by ligation-mediated PCR). DNA is digested in parallel with MspI (resistant to DNA methylation), and then the HpaII and MspI products are amplified by ligation-mediated PCR and hybridized using separate fluorochromes to a customized array. The analysis of HELP data involves quality analysis and normalization. The methods described in Thompson et.al (127) will be used to identify epigenetics signatures which are different between patients who relapsed and patients who did not relapse. Signatures identified by epigenetic analysis will be correlated with DFS using a LARS/LASSO approach (128,129) for each maintenance arm. For the gene expression data, we will use Dchip software to normalize the expression levels and generate model-based expression intensities. Genes will be filtered by examining ratios of standard deviation to the mean. Genes will be hierarchically clustered to find genes with high/low fold change/differences. Supervised analyses will be used to identify genes that are differentially expressed between patients who relapsed and patients who did not relapsed. Genes or epigenetic signatures identified by gene expression or epigenetic analysis will be correlated with DFS using LARS/LASSO approach (128,129).

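### Section 8.3.5 conflicts with Sections 3.2.8.7, 5.1.8.1 and 5.4.3 on when to hold, reduce or stop decitabine maintenance

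*Combined protocol and SAP*

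**What the plan says.** Four places in the combined protocol and SAP give rules for decitabine in Arm F.

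- **Section 3.2.8.7** (maintenance criteria) requires ANC above 1000 and platelets above 75,000 "prior to starting every cycle of treatment with decitabine. Decitabine may be delayed for up to 4 weeks between cycles" while counts recover, so cycles can be as much as 8 weeks apart.
- **Section 5.1.8.1** (treatment plan) repeats that count rule. It adds that patients who cannot keep to schedule, within the allowed delay, "due to cytopenias or persistent side effects will discontinue decitabine and subsequently be observed per the" Arm E group. They are still analysed as Arm F.
- **Section 5.4.3** (dose modifications) repeats the stop rule and says "There are no planned dose reductions in decitabine"; 5.1.8.1 says the same.
- **Section 8.3.5** (dose specifics) names four conditions: marrow cellularity of 5% or less, a clear rise in marrow blasts, neutropenic fever, or a systemic neutropenic infection that has not cleared. If none is present, the text runs "dosing should be continued at the recommended dose without delay. In the event of delayed recovery to pre-dose ANC and platelet counts". The consequence it attaches, once slow recovery has persisted beyond two cycles, is that "the dose should be reduced by approximately 25% upon restarting therapy".

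Section 8.3.5 points to 5.4.3 for duration only. Nothing in the documents says which section takes precedence.

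**The concern.** A site treating an Arm F patient with low counts can find two different instructions, depending on the section it opens. One holds a myelosuppressive drug until fixed counts are met and stops it if recovery takes too long. The other gives no ANC or platelet level below which a cycle must wait, and answers repeated slow recovery with a smaller dose.

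Two things are at stake. The first is safety: these are patients aged 60 or over in remission, and 8.3.5 can be read to allow a cycle at counts where 3.2.8.7 forbids one. The second is the definition of the experimental arm: the same blood count can send a patient to observation or keep her on drug, so Arm F may not be one regimen across sites.

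**Working it through.** No sample size, power, alpha or event count depends on this point. The check is to apply both sets of rules to the same patient and see whether both can be followed.

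**Inputs.** Planned dose 20 mg/m²/day for 3 days every 4 weeks (5.1.8.1, 8.3.5); count thresholds and allowed delay (3.2.8.7, 5.1.8.1); stop and no-reduction rules (5.1.8.1, 5.4.3); the four conditions and the 25% cut (8.3.5).

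| Situation when the next cycle is due | 3.2.8.7, 5.1.8.1, 5.4.3 | 8.3.5 |
|---|---|---|
| A. ANC 800, platelets 60,000, afebrile, marrow not hypoplastic, no rise in blasts | Hold: both counts are below threshold | None of the four conditions is met, so the cycle may be given on time at 20 mg/m²/day |
| B. Slow recovery for more than two cycles, each time within 4 weeks | Full dose, 20 mg/m²/day | Restart at 20 × (1 − 0.25) = 15 mg/m²/day |
| C. Recovery takes longer than the allowed 4-week delay | Stop and observe as Arm E | No stop rule; after more than two delayed recoveries, restart at about 15 mg/m²/day |

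In B and C the instructions cannot both be obeyed. In A they cannot both be obeyed if the first sentence of 8.3.5 is taken as it stands.

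**The yardsticks differ too.** Sections 3.2.8.7 and 5.1.8.1 use fixed counts. Section 8.3.5 uses the patient's own pre-dose counts. A patient above 75,000 but short of her own pre-dose level is ready for full dose under the first and may count as a delayed recovery under the second.

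**Situation A is foreseeable.** Section 3.2.8.2 admits patients in CRi to maintenance, and Section 6.2 defines CRi by platelets above 50 × 10⁹/L without further recovery. Platelets of 50,000 to 75,000 can therefore occur in this population before any decitabine is given.

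**Whether 8.3.5 defers to Section 5.** The parallel sections for cytarabine (8.1.5) and daunorubicin (8.2.5) refer to 5.4.1 and 5.4.2 for dose modification. Section 8.3.5 refers to 5.4.3 for duration, which 5.4.3 does not state in total, and then gives a modification rule of its own.

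**Reach of a text change.** Section 9.5 reports 120 patients already in the second randomisation against a goal of 172, so 172 − 120 = 52 could still enter. With the equal split assumed in 9.8 (86 per arm), about 52 / 2 = 26 of them would be in Arm F. Section 9.5 reopens the study only if conditional power exceeds 0.7.

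**The case against.** The strongest reply is that a careful site would not be misled. Eligibility, treatment plan and dose modifications all agree with each other. The count rule is worded as mandatory and sits in the eligibility checklist, whereas 8.3.5 is worded as a recommendation in a chapter on drug formulation and procurement. The second sentence of 8.3.5 also speaks of restarting therapy, which implies that the drug had been held for counts. And the documents give no sign that any site has dosed from 8.3.5.

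Much of this stands. A reader might infer that 8.3.5 forbids holding for low counts altogether; its reference to restarting does not support that. The fair reading is that 8.3.5 leaves low counts out of its reasons to wait and supplies no threshold, so a site may treat where 5.1.8.1 says hold.

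The reply does not remove the conflict. There is no precedence clause, and no weighing of mandatory against advisory wording reconciles a 25% cut with a statement that no reductions are planned.

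**Conclusion.** The conflict is real and is in the current text. It concerns safety and the consistency of treatment in Arm F. Intention-to-treat assignment, type I error and the stated power are untouched. Its size can be stated only per patient: treat or hold in situation A, and about 15 mg/m²/day against full dose or stopping in B and C.

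Four stronger inferences are tempting but not supported:

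- **A cumulative-dose ratio between the two rule sets.** Any such figure depends on whether 8.3.5 is taken to allow holding and on what counts as a delayed recovery. The text settles neither.
- **A count of affected patients from the decitabine adverse event list in 5.3.** That list pools trials and includes all grades. It does not say how many patients fall below 1000 or 75,000.
- **A share of cycles given without a recent marrow.** Section 7.1 says "Routine bone marrow aspirate and biopsy is required every 3 months during maintenance and observation", but 8.3.5 does not require a marrow before each cycle and no section defines how recent one must be.
- **A bias in the DFS result of known size.** The documents give no dose-effect relation for maintenance.

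The practical reach is limited. A text change helps patients still on decitabine and, only if the study reopens, up to 52 further randomised patients. For cycles already given, only reporting can help.

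**What to change.** Replace the second paragraph of 8.3.5 with a cross-reference to 5.1.8.1 and 5.4.3: ANC above 1000 and platelets above 75,000 before each cycle, wait up to 4 weeks, then stop, with no dose reduction. Keep neutropenic fever and uncleared infection as added reasons to hold. Notify sites. In the final report, list Arm F cycles started below the count rule and any reduced doses, so that readers can see what the first 120 randomised patients received.

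Do not use this edit to require the counts at the second randomisation. That would be a separate eligibility change, and it would exclude CRi patients with platelets of 50,000 to 75,000 from both arms.

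The cost is one paragraph, a site notice and a short listing. The downside is that some patients will stop decitabine earlier than they would under 8.3.5.
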